7.2 Recording of Adverse Events

At each contact with the subject, the investigator will seek information on solicited adverse events by specific questioning and, as appropriate, by examination. Information on all solicited adverse events will be recorded immediately in the source document, and also in the appropriate adverse event module of the case report form (CRF). All clearly related signs, symptoms, and abnormal diagnostic procedures results should be recorded in the source document, though should be grouped under one diagnosis. These will be graded using the Common Toxicity Criteria Adverse Events (CTCAE) v4.0 of the National Cancer Institute. Retrospective review of patient charts will be employed to assure accurate recording of solicited adverse events. Any additional solicited adverse events identified by such retrospective review will be incorporated into the data base and included in the analysis.

All solicited adverse events occurring during the study period will be recorded. The clinical course of each event will be followed until resolution, stabilization, or until it has been determined that the study treatment or participation is not the cause. Serious adverse events that are still ongoing at the end of the study period will be followed up to determine the final outcome. Any serious adverse event that occurs after the study period and is considered to be possibly related to the study treatment or study participation will be recorded and reported immediately.

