3.2 Exclusion Criteria

Patients with the following conditions are not eligible to participate in this trial:

- Pregnant women or women of childbearing potential without adequate contraception. Contraception, which can include abstinence, is required since the last menstrual period until completion of SRS.
- Evidence of pneumothorax
 - Untreated pneumothorax risks tension pneumothorax during ascent in HBO chamber
- COPD with CO₂ retention
 - Such patients can develop respiratory depression as HBO reduces their hypoxic drive
- Uncontrolled seizure disorder
 - Note that patients on adequate antiepileptic medications may receive HBO
- Claustrophobia resistant to medication
 - Pre-medication with anxiolytics is generally sufficient for almost all anxious patients undergoing HBO treatment
- History of middle ear surgery
 - Failure to equalize pressure in the middle ear can cause displacement of middle ear structures with consequent hearing loss
 - To clarify: placement of a tympanostomy tube is not a contraindication to HBO, and in fact may improve tolerability of the procedure
- History of bleomycin administration
 - HBO can exacerbate interstitial pneumonitis in such patients
- Current cis-platinum chemotherapy (i.e. therapeutic levels in the bloodstream at the time of HBO therapy)
 - HBO can increase cytotoxicity of cis-platinum
- Uncontrolled high blood pressure
 - HBO can increase systemic vascular resistance
- Unstable angina or myocardial infarction within the previous 3 months
 - Increased afterload due to HBO can increase myocardial workload
- Cardiac EF ≤ 35%
 - Pulmonary edema can arise with HBO in certain patients with severe heart failure
 - In patients with prior history of CHF, subsequent echocardiogram and ECG are required to establish EF>35%
- Treatment with disulfiram

- Disulfiram inhibits superoxide dismutase and is not approved for use concomitantly with hyperbaric oxygen therapy
- Active drug/alcohol dependence or abuse
- Lack of adequate social support structures, e.g. homelessness
- Tumors with potential confounding results on serum marker studies
 - Small cell (neuroendocrine) carcinomas
 - Carcinoid tumors

3.3 *Subject Recruitment and Screening*

Subjects will be recruited from patients who are potential candidates for SRS treatment at DHMC for brain metastases. Such patients are referred to radiation oncology by practitioners at DHMC and by physicians at outlying hospitals.

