All solicited adverse events that do not meet any of the criteria for serious will be regarded as **non-serious solicited adverse events**.

Adverse Event Reporting Period

The study period during which solicited adverse events must be reported is defined as the period from the initiation of any study procedures to the end of the study treatment

follow-up. For this study, the study treatment follow-up is defined as the time following study treatment until the date of documented death, withdrawal of consent, or the end of the study, whichever occurs first.

Preexisting Condition

A preexisting condition is one that is present at the start of the study. A preexisting condition will be recorded as a solicited adverse event if the frequency, intensity, or the character of the condition worsens during the study period.

General Physical Examination Findings

At screening, any clinically significant abnormality will be recorded as a preexisting condition. At the end of the study, any new clinically significant findings/abnormalities that meet the definition of an adverse event must also be recorded and documented as an adverse event.

Post-study Adverse Event

All unresolved solicited adverse events will be followed by the investigator until the events are resolved, the subject is lost to follow-up, or the solicited adverse event is otherwise explained. At the last scheduled visit, the investigator will instruct each subject to report any subsequent event(s) that the subject, or the subject's personal physician, believes might reasonably be related to participation in this study. The investigator will notify the study sponsor of any death or adverse event occurring at any time after a subject has discontinued or terminated study participation that may reasonably be related to this study. The sponsor will also be notified if the investigator becomes aware of the development of cancer or of a congenital anomaly in a subsequently conceived offspring of a subject that has participated in this study.

Abnormal Laboratory Values

A clinical laboratory abnormality will be documented as an adverse event if any one of the following conditions is met:

- The laboratory abnormality is not otherwise refuted by a repeat test to confirm the abnormality
- The abnormality suggests a disease and/or organ toxicity

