- The abnormality is of a degree that requires active management; e.g. change of dose, discontinuation of the drug, more frequent follow-up assessments, further diagnostic investigation, etc.

Hospitalization, Prolonged Hospitalization or Surgery

Any solicited adverse event that results in hospitalization or prolonged hospitalization will be documented and reported as a serious adverse event unless specifically instructed otherwise in this protocol. Any condition responsible for surgery will be documented as a serious adverse event if the condition meets the criteria for a solicited adverse event.

Neither the condition, hospitalization, prolonged hospitalization, nor surgery will be reported as an adverse event in the following circumstances:

- Hospitalization or prolonged hospitalization for diagnostic or elective surgical procedures for a preexisting condition. Surgery should **not** be reported as an outcome of an adverse event if the purpose of the surgery was elective or diagnostic and the outcome was uneventful.
- Hospitalization or prolonged hospitalization required to allow efficacy measurement for the study.
- Hospitalization or prolonged hospitalization for therapy of the target disease of the study, unless it is a worsening or increase in frequency of hospital admissions as judged by the clinical investigator.

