7.4 Stopping Rules

An internal stopping rule is set in place whereby the study will be terminated if (1) feasibility appears unattainable, or (2) a significant number of patients experience a significant adverse event (SAE) as outlined above:

- Regarding the primary endpoint of feasibility, we anticipate a steep learning curve for treatment of patients on this trial. The overall goal is to begin SRS within 15 minutes of exiting the HBO chamber; however, it is known that oxygen levels remain elevated in the brain up to 30 minutes after HBO treatment. The following stopping rules will be applied:
 - Analysis after enrollment of first 10 patients demonstrates no more than two patients (20%) treated within 30 minutes of HBO chamber exit.
 - Analysis after enrollment of first 15 evaluable patients demonstrates no more than five patients (33%) treated within 30 minutes of HBO chamber exit.
- Regarding the secondary endpoint of noninferiority, every patient who receives treatment on this protocol will be evaluated at every patient encounter for adverse events. Toxicities will be graded using the Common Toxicity Criteria Adverse Events (CTCAE) v4.0 of the National Cancer Institute.
 - Overall incidence of adverse events in this study will be reviewed every three months.
 - At time of any such review, if more than 40% of enrolled patients (minimum of 5 patients) experience SAEs that are deemed likely related to the protocol treatment (HBO combined with SRS), then the study will be terminated (i.e. more than 2 out of 5 patients, or more than 4 out of 10 patients, for example).
 - Note that some SAEs are expected in this patient population, given the nature of the disease process that is being treated. The stopping rule of 40% was elected as representing an incidence level significantly higher than that expected routinely in this patient population.
- It is the responsibility of the Principal Investigator to oversee the safety of the study. This safety monitoring will include careful assessment and appropriate reporting of adverse events as noted above, as well as quarterly review by the Norris Cotton Cancer Center Data and Safety Monitoring and Accrual Committee (see section 9 Auditing, Monitoring and Inspecting). Medical monitoring will include a regular assessment of the number and type of serious adverse events.

8 Data Handling and Record Keeping

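### The SAE definition and the stopping rule cover any adverse event, but in-study recording is written for solicited events only, so an unlisted treatment-related SAE may not reach the 40% count

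*Combined protocol and SAP*

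**What the plan says.** Two scopes run through Sections 7.1 to 7.4.

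**Any adverse event.** Section 7.1 defines an adverse event broadly and calls any such event serious if it meets one of six criteria, one of which is needing or prolonging a hospital stay. Section 7.4 has every treated patient evaluated for adverse events at each encounter. It adds "Overall incidence of adverse events in this study will be reviewed every three months" and terminates the study if more than 40% of enrolled patients (minimum of 5) have SAEs judged likely related to the combined treatment.

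**Solicited events only.** Section 7.2 says that at each contact "the investigator will seek information on solicited adverse events by specific questioning and, as appropriate, by examination", that "Retrospective review of patient charts will be employed to assure accurate recording of solicited adverse events", and, in summary, "All solicited adverse events occurring during the study period will be recorded". Entry in the source document and the case report form (CRF) is likewise specified for solicited events. In 7.1 the reporting period has the same limit: "The study period during which solicited adverse events must be reported is defined as the period from the initiation of any study procedures". So does the hospitalization paragraph: "Any solicited adverse event that results in hospitalization or prolonged hospitalization will be documented and reported as a serious adverse event". The sentence on surgery that follows is tied to solicited events too.

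**The list.** Attachment 14.6 gives an open entry to the nervous-system and eye headings. The cardiac heading holds only heart failure, and the respiratory heading only pneumothorax and sinus pain. The ear entry is fixed to barotrauma. Section 3.2 meanwhile names further HBO effects, among them "HBO can exacerbate interstitial pneumonitis in such patients" and "Increased afterload due to HBO can increase myocardial workload".

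**The concern.** A stopping rule is only as good as the data that reach it. The rule in 7.4 needs every likely related SAE, but the section that tells staff what to ask about, enter and look for in the charts supplies solicited events. If staff follow 7.2 literally, a mid-study admission for, say, pneumonitis or a new coronary event is covered by the definition in 7.1 but by no explicit instruction to record it. The quarterly review could then work from an incomplete count, and the toxicity reported for a combination that Section 1.4 itself calls novel could be understated.

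**Working it through.** **1. Is there an in-study recording instruction for an unlisted SAE?**
- 7.1, SAE definition: covers it, but a definition creates no duty to record.
- 7.1, reporting period and hospitalization paragraph: solicited events only.
- 7.1, other paragraphs: worsened preexisting conditions, qualifying laboratory abnormalities and new findings at the end of the study are captured. A new acute clinical event mid-study is not addressed.
- 7.2: questioning, CRF entry and chart review cover solicited events only. SAEs still ongoing at study end are followed, and possibly related SAEs arising after the study period are recorded and reported. There is no matching sentence for unsolicited SAEs arising during the study.
- 7.3: not limited to solicited events, but an event must be related, unexpected and serious. In 7.1, unexpected is explained as not described in study documents such as the protocol. The omitted effects are described in 3.2, so they may fail that test.
- 7.3.1: defers to IRB and institutional policy.
- 7.4: evaluates patients for adverse events without the solicited limit, which conflicts with 7.2.

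**2. Which HBO effects named in 3.2 are missing from 14.6?** Respiratory depression, interstitial pneumonitis, raised systemic vascular resistance (hypertension is not listed) and increased myocardial workload (angina and infarction are not listed). Pulmonary edema is not named but is partly covered by heart failure. Hearing loss is not named; the ear entry is barotrauma.

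**3. The plan's own boundary.** Stop when the number of patients with a likely related SAE exceeds 0.40 × n:
- n = 5: 0.40 × 5 = 2, so stop at 3.
- n = 10: 0.40 × 10 = 4, so stop at 5.
- n = 15: 6, so stop at 7.
- n = 20: 8, so stop at 9.

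The first two match the examples in 7.4. One uncounted patient changes 3/5 = 60% (stop) to 2/5 = 40% (continue), or 5/10 = 50% (stop) to 4/10 = 40% (continue).

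**4. Direction of the effect (illustration only).** Let p be the true proportion of patients with a likely related SAE and c the share of those patients who have at least one such SAE captured. The rule then sees p × c. The chance of stopping is the sum, over looks, of the exact binomial probability of first exceeding the boundary at that look. The documents give neither p nor c, and reviews are quarterly rather than tied to patient numbers, so p, c and the looks are all assumed.

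| True p | Captured c | Seen p × c | Looks at 5, 10, 15, 20 | Look after every patient, 5 to 20 |
|---|---|---|---|---|
| 0.40 | 1.0 | 0.40 | 0.58 | 0.75 |
| 0.40 | 0.9 | 0.36 | 0.45 | 0.64 |
| 0.40 | 0.8 | 0.32 | 0.33 | 0.52 |
| 0.10 | 1.0 | 0.10 | 0.010 | 0.028 |
| 0.10 | 0.8 | 0.08 | 0.005 | 0.015 |

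The chance of stopping falls in every comparison, as it must, because a missed patient can only lower the count. The amount depends entirely on the assumptions: large near the threshold, about one percentage point or less at a low true rate.

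**The case against.** A reader might infer that an admission becomes an SAE only if the event is on the solicited list, so that the stopping rule excludes unlisted harms. The documents do not support that. The general definition in 7.1 makes any adverse event that needs or prolongs a hospital stay serious. The hospitalization paragraph adds a directive for solicited events and does not say that other admissions are not SAEs. Its stated exceptions concern elective or diagnostic procedures, efficacy measurement and treatment of the target disease. Section 7.4 evaluates patients for adverse events generally and adds regular assessment of the number and type of SAEs with quarterly committee review, and the reporting criteria in 7.3 are not tied to the list. This objection stands: the fault is conflicting wording, not a rule that shuts out unlisted SAEs.

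It is also fair that the omitted effects are named in 3.2 mainly as reasons to exclude patients at risk, that exposure is one 30-minute session, and that the main HBO risks in Section 1.5 are on the list (claustrophobia only through anxiety). This lowers the likely number of missed events but does not bring it to zero. The criteria exclude uncontrolled hypertension, unstable angina or infarction within 3 months, and COPD with CO2 retention. They do not exclude controlled hypertension, older infarction or COPD without retention.

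Finally, the probabilities above should not be read as an estimate of this trial's loss. The rule counts patients, so someone with any captured related SAE still counts, and no capture rate can be taken from the documents. Soliciting a fixed list for non-serious events is a legitimate design choice.

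**Conclusion.** The concern holds as an inconsistency to be reconciled. The SAE definition and the stopping rule cover any adverse event. The instructions that generate the data, and the hospitalization and surgery paragraph, are written for solicited events, and the list leaves out HBO effects that the protocol itself names. An unlisted treatment-related SAE during the study may therefore not be recorded consistently for the 40% rule. How many events this could affect cannot be derived from the documents. What can be said is that the error runs in one direction, towards not stopping, and that at 3 of 5 or 5 of 10 a single missed patient is enough to matter. The change should be made because it is cheap and protects the trial's only SAE-based stopping rule, not because a material loss has been shown.

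**What to change.** In 7.1 (the reporting-period and hospitalization/surgery paragraphs) and in 7.2, state that all serious adverse events, solicited or not, are recorded from the first study procedure and counted in the 7.4 review. Keep the solicited list as the scope for non-serious events. In 14.6, add an open line for other, specified events under the cardiac and respiratory headings, and carry it into the CRF. The cost is protocol and CRF wording, plus slightly more recording in about 20 patients. The stopping boundary and sample size do not change.

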7.3 Reporting of Serious Adverse Events and Unanticipated Problems

Adverse events that will be reported are those that are:

- At least possibly related to study participation,
- unexpected, and
- serious or involve risks to subjects or others
(see definitions, section 7.1).

The following information will be included in the adverse event report initial report:

- Study identifier
- Subject number
- A description of the event
- Date of onset
- Current status
- Whether study treatment was discontinued

- The reason why the event is classified as serious
- Investigator assessment of the association between the event and study treatment

7.3.1 Investigator reporting: notifying the IRB

Serious adverse events will be reported to the Dartmouth-Hitchcock Health (D-HH) IRB as required per IRB and institutional policy.

7.4 Stopping Rules

An internal stopping rule is set in place whereby the study will be terminated if (1) feasibility appears unattainable, or (2) a significant number of patients experience a significant adverse event (SAE) as outlined above:

- Regarding the primary endpoint of feasibility, we anticipate a steep learning curve for treatment of patients on this trial. The overall goal is to begin SRS within 15 minutes of exiting the HBO chamber; however, it is known that oxygen levels remain elevated in the brain up to 30 minutes after HBO treatment. The following stopping rules will be applied:
 - Analysis after enrollment of first 10 patients demonstrates no more than two patients (20%) treated within 30 minutes of HBO chamber exit.
 - Analysis after enrollment of first 15 evaluable patients demonstrates no more than five patients (33%) treated within 30 minutes of HBO chamber exit.
- Regarding the secondary endpoint of noninferiority, every patient who receives treatment on this protocol will be evaluated at every patient encounter for adverse events. Toxicities will be graded using the Common Toxicity Criteria Adverse Events (CTCAE) v4.0 of the National Cancer Institute.
 - Overall incidence of adverse events in this study will be reviewed every three months.
 - At time of any such review, if more than 40% of enrolled patients (minimum of 5 patients) experience SAEs that are deemed likely related to the protocol treatment (HBO combined with SRS), then the study will be terminated (i.e. more than 2 out of 5 patients, or more than 4 out of 10 patients, for example).
 - Note that some SAEs are expected in this patient population, given the nature of the disease process that is being treated. The stopping rule of 40% was elected as representing an incidence level significantly higher than that expected routinely in this patient population.
- It is the responsibility of the Principal Investigator to oversee the safety of the study. This safety monitoring will include careful assessment and appropriate reporting of adverse events as noted above, as well as quarterly review by the Norris Cotton Cancer Center Data and Safety Monitoring and Accrual Committee (see section 9 Auditing, Monitoring and Inspecting). Medical monitoring will include a regular assessment of the number and type of serious adverse events.

8 Data Handling and Record Keeping

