3.4.1 When and How to Withdraw Subjects

Reasons for treatment discontinuation include:

- Subject request or withdrawal of consent
- Subject non-compliance with the protocol
- Life-threatening or unacceptable adverse events at time of SRS or HBO treatment, such as HBO-induced seizure
- Physician judgment in view of subject's inter-current illness or safety considerations
- Administrative decision to discontinue the study.

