7.1 Definitions

Unanticipated Problems Involving Risk to Subjects or Others

Any incident, experience, or outcome that meets all of the following criteria:

- Unexpected in nature, severity, or frequency (i.e. not described in study-related documents such as the IRB-approved protocol or consent form, the investigators brochure, etc)

- Related or possibly related to participation in the research (i.e. possibly related means there is a reasonable possibility that the incident experience, or outcome may have been caused by the procedures involved in the research)
- Suggests that the research places subjects or others at greater risk of harm (including physical, psychological, economic, or social harm).

Adverse Event

An **adverse event** (AE) is any symptom, sign, illness or experience that develops or worsens in severity during the course of the study. Inter-current illnesses or injuries should be regarded as adverse events. Abnormal results of diagnostic procedures are considered to be adverse events if the abnormality:

- results in study withdrawal
- is associated with a serious adverse event
- is associated with clinical signs or symptoms
- leads to additional treatment or to further diagnostic tests
- is considered by the investigator to be of clinical significance

Solicited Adverse Event

A **solicited adverse event** is any adverse event that has been identified by the PI or co-PIs as potentially related to intracranial SRS and/or HBO treatments. Occurrence and severity of all solicited adverse events will be catalogued for all D12129 patients. These are enumerated in Attachment 14.6.

Serious Adverse Event

Adverse events are classified as serious or non-serious. A **serious adverse event** is any AE that is:

- fatal
- life-threatening
- requires or prolongs hospital stay
- results in persistent or significant disability or incapacity
- a congenital anomaly or birth defect
- an important medical event

Important medical events are those that may not be immediately life threatening, but are clearly of major clinical significance. They may jeopardize the subject, and may require intervention to prevent one of the other serious outcomes noted above. For example, drug overdose or abuse, a seizure that resulted in in-patient hospitalization, or intensive treatment of bronchospasm in an emergency department would typically be considered serious.

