9.1 Safety and Data Monitoring

This study will be monitored by the Data Safety Monitoring and Accrual Committee (DSMAC) of the Norris Cotton Cancer Center. The Committee meets quarterly to review accrual rates and information of all studies that have accrued participants. The DSMAC has the authority to suspend or terminate all research activities that fall within its jurisdiction. In the event that a study is suspended or terminated by the DSMAC, that information will be forwarded to the D-HH IRB.

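### Section 7.4's only numeric toxicity trigger ignores severity and needs at least three affected patients, so one or two treatment-related deaths do not by themselves require a pause

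*Combined protocol and SAP*

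**What the plan says.** Section 7.4 of the combined protocol and SAP provides for three-monthly reviews of adverse events and attaches one numeric toxicity criterion for ending the study: "At time of any such review, if more than 40% of enrolled patients (minimum of 5 patients) experience SAEs that are deemed likely related". The treatment meant is HBO combined with SRS. Its worked examples are "more than 2 out of 5 patients, or more than 4 out of 10 patients, for example". The other numeric triggers in 7.4 concern feasibility (time from chamber to beam-on).

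Section 7.1 defines an SAE by a single list. Fatal and life-threatening events stand in it beside an event that "requires or prolongs hospital stay", and 7.4 does not separate them.

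Other provisions bear on safety:

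- Section 7.4 makes the principal investigator responsible for safety and adds: "Medical monitoring will include a regular assessment of the number and type of serious adverse events".
- Section 9.1 says of the monitoring committee (DSMAC): "The Committee meets quarterly to review accrual rates and information of all studies that have accrued participants". It gives the committee power to suspend or close a study, but names no event that obliges it to act.
- Section 3.4.1 lists a life-threatening event at treatment as a reason to discontinue that subject, and also lists "Administrative decision to discontinue the study".
- Section 7.3 calls for a report when an event is unexpected, is serious or carries risk, and is "At least possibly related to study participation".
- Section 7.3.1 sends SAEs to the IRB "as required per IRB and institutional policy".
- Sections 1 and 10 bind the study to GCP, FDA rules and institutional policy. None of these is reproduced.

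**The concern.** A proportion-based rule suits events that are expected at some background frequency, and 7.4 defends 40% on that ground. It does not suit a rare event of the gravest kind. Under the rule, a related death counts the same as a related SAE that lengthened an admission by a day.

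The setting makes this relevant. Sections 1.1 and 1.4 present HBO before SRS as a new combination without earlier studies. The centre's reassuring experience (Section 1.4) was with fully fractionated head-and-neck treatment over seven weeks, whereas here 12 to 20 Gy is given to the target margin in one session (Section 5.3.7). Section 1.5 reports an odds ratio of 2.43 (CI 1.43 to 4.12) for radiation complications with HBO in earlier head-and-neck trials, although it attributes this largely to radiation technique and dose per fraction.

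At stake is whether the next patient is treated before anyone has been obliged to look at a related death. Because treatment is a single session, discontinuing the affected subject does nothing for the next one.

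**Working it through.** **Inputs.** Threshold above 40%, at least 5 enrolled, reviews every three months (7.4); 20 patients planned (6.2), accrued over 36 months (6.1); seizure rate 0.06% per dive in the general HBO population (1.5).

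**Step 1: reproduce the plan's own figures.** The smallest whole number k with k/n > 0.40 is floor(0.4n) + 1.
- n = 5: floor(2.0) + 1 = 3, which is more than 2 of 5.
- n = 10: floor(4.0) + 1 = 5, which is more than 4 of 10.

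Both match 7.4. The first example also settles that the minimum of five refers to patients enrolled, not patients affected.

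**Step 2: the full boundary.**

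| Enrolled | Affected patients needed |
|---|---|
| 1-4 | rule inactive |
| 5-7 | 3 |
| 8-9 | 4 |
| 10-12 | 5 |
| 13-14 | 6 |
| 15-17 | 7 |
| 18-19 | 8 |
| 20 | 9 |

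**Step 3: one or two affected patients.** From n = 5 on, one patient is at most 1/5 = 20% and two are at most 2/5 = 40%, which does not exceed 40%. Neither meets the rule at any enrolment, including beyond 20 if withdrawn patients are replaced (3.4.3). Other related SAEs would add to the count.

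**Step 4: timing.** Assume even accrual, 36/20 = 1.8 months per patient, and reviews counted from the start of accrual.
- First patient at month 0: five are enrolled by month 7.2, so the first review at which the rule can fire is month 9.
- First patient at month 1.8: the fifth is enrolled at 5 × 1.8 = 9.0 months. The first such review is month 9 if a patient enrolled that day counts, and month 12 if not.

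Between reviews 3/1.8 = 1.67 patients are enrolled on average, that is, one or two.

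**Step 5: how often a severity trigger might act.** The documents give no rate of related fatal or life-threatening SAEs. The seizure figure covers one event type of any outcome. The other rates are assumptions. The chance of at least one event in m patients is 1 − (1 − p)^m.

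| Rate p | First 4 patients | 20 patients | Expected affected, 20p |
|---|---|---|---|
| 0.06% (seizure, 1.5) | 0.24% | 1.2% | 0.012 |
| 1% (assumed) | 4% | 18% | 0.2 |
| 2% (assumed) | 8% | 33% | 0.4 |
| 5% (assumed) | 19% | 64% | 1.0 |

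The 20-patient columns are approximate. Replacement of withdrawn patients could raise the number treated above 20, while an event that becomes known after the last treatment would hold nothing.

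**Step 6: is a hold mandatory elsewhere?** Section 7.4 has SAE type assessed but attaches no action. Section 9.1 gives power without a trigger. Section 3.4.1 acts on the subject or rests on a decision. Sections 7.3 and 7.3.1 require reporting. The plan for a seizure in the chamber (4.3) concerns that patient's care. None of these requires a study hold.

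**The case against.** The 40% criterion is a rule for terminating the study, not for pausing it. A reader might infer that the protocol orders treatment to continue below 40%, or that related deaths would go unexamined. The documents support neither inference. Being silent on a pause is different from forbidding one; SAE type is assessed, the committee reviews quarterly and may suspend, and events in the first four patients count in full once five are enrolled.

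A reader might also infer that no mandatory hold exists at all. That cannot be said, because the IRB, GCP and institutional policies that the protocol cites are not shown and may contain one.

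The expected risk may also be low. Section 1.1 cites little normal-tissue toxicity in glioma studies, 1.5 describes 2.4 ATA as safe, Section 3.2 screens out many HBO hazards, and an air test dive precedes treatment. The only rate taken from the documents gives about 1% in 20 patients. With one or two patients enrolled between reviews, the gain over existing review is modest, and any new trigger still rests on a judgement that the event is likely related.

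These points stand. They limit the weight of the concern and make it an optional safeguard rather than a defect. They do not supply a required response to a related death, and the rationale for 40%, that some SAEs are expected in this population, does not explain why a likely related death needs no separate response.

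**Conclusion.** The point holds as a cheap improvement. The one numeric toxicity trigger takes no account of severity and needs at least three affected patients, so one or two treatment-related deaths do not by themselves require any pause. The supplied documents contain no mandatory hold after such an event; the safeguards they describe are discretionary, or depend on policies that cannot be seen.

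The boundary is exact and agrees with the plan's own examples. Under even accrual the 40% rule cannot fire before about month 9 to 12. How often a severity trigger would matter is unknown: the 1%, 2% and 5% rates are illustrations only. The primary feasibility analysis is unaffected. Confidence is medium, mainly because of the unseen policies.

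**What to change.** Keep the 40% rule and its three-monthly timing. Add to Section 7.4: *From the first patient on, any fatal or life-threatening SAE deemed likely related to HBO-SRS holds further protocol treatments until the DSMAC has reviewed the case out of cycle.*

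This is one sentence, and it uses the existing committee, the 7.1 categories and the 7.4 attribution wording. The cost is a possible hold, plus an ad hoc review by a committee that is described as meeting quarterly. If no ad hoc review can be arranged, a hold could last up to about three months, which at planned accrual delays one or two patients. At the assumed rates, about 0.2, 0.4 or 1.0 affected patients are expected per 20 treated, and slightly more if withdrawn patients are replaced. If IRB or institutional policy already requires such a hold, citing it in 7.4 would do instead.
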